6.5.1 Dose Modifications

If a study drug-related AE occurs in a patient that the Investigator judges as presenting a potential risk to the patient for further dosing, the fitusiran dose may be held at the discretion of the Investigator, at which time the study Medical Monitor should be contacted.

6.5.1.1 LFT Criteria for Withholding, Monitoring and Stopping Fitusiran Dosing

- 1. It is preferable that LFT results are to be obtained by Central laboratory. If not available, local laboratory results may be used; however, if a local assessment is drawn, a biochemistry sample must also be drawn for analysis at the central laboratory.
- 2. For patients following the SoAs in Table 1 and Table 2:
 - a) For up to 2 years, LFT results are to be obtained within 7 days prior to dosing and results are to be reviewed prior to each dose of fitusiran.
 - b) From Year 3 onwards, the frequency of predose LFT monitoring may be decreased for patients who have negative hepatitis C antibody titers and who meet following specific criteria:
 - Did not have any ALT elevation $>3 \times$ ULN persisting for ≥ 2 consecutive months at any time during the previous 12 months.
 - Did not have any fitusiran doses held due to LFT elevations during the study.

Note: negative Hep C patients include patients who never met HCV, ie, antibodies are negative, but also those with only positive antibodies without any viral load detected (ie, patient has cleared the infection, but antibodies still detected as positive). To confirm this eligibility, patients who cleared Hep C infection must have documented sustained negative virologic load.

3. For patients on a monthly dosing schedule following the SoA in Table 3 (modified IMP regimen SoA), monthly predose LFT testing is not required if the criteria for reduced predose LFT monitoring is met as described below:

- Did not have any ALT elevation $>3 \times$ ULN persisting for ≥ 2 consecutive months at any time during the first 12 months under this regimen.
- Must not have had any fitusiran doses held during the first 12 months under this regimen.
- 4. For patients on a every other month dosing schedule following the SoA in Table 3 (modified IMP regimen SoA), monthly testing is required for the first 12 months under the dosing regimen. After the first year, predose LFT testing is only required every other month prior to dosing.
- 5. For any ALT elevation >3× ULN or >3× Baseline (for those with elevated baseline values), central laboratory results should be used to guide subsequent monitoring as detailed in Table 9.
- 6. For any ALT elevation >3× ULN or >3× Baseline (for those with elevated baseline values) (Table 9):
 - a) Confirm using central laboratory, as soon as possible, ideally within 2 to 3 days, but no later than 7 days.
 - a) Perform assessments per Table 10 and Table 11.
 - b) If an alternative cause is found, provide appropriate care.
- 7. For any ALT elevation >3× ULN or >3× Baseline without alternative cause see Table 9 below:

Table 9: Monitoring and Dosing Rules for Patients with Confirmed ALT Elevations >3× ULN or >3× Baseline with No Alternative Cause Identified Transaminase **HCV RNA Negative Patients HCV RNA Negative Patients with HCV RNA Positive Patients with HCV RNA Positive Patients** Level with Normal Baseline ALT Normal Baseline ALT Elevated Baseline ALTa with Elevated Baseline ALT^{a, b} Discontinue dosing when ALT $>3 \times$ Discontinue dosing when $>3\times$ to Discontinue dosing when 5×ULN or ALT>3×ULN if patient is Baseline or >300 U/L (whichever ALT $>3 \times$ Baseline or >300 U/L comes first) if patient is (whichever comes first) if patient Baseline symptomatic^C, TBL $\geq 2 \times ULN$, or symptomatic^c, TBL >2×ULN, or INR >1.5. is symptomatic^C, Otherwise, may continue dosing INR >1.5. TBL $>2 \times$ ULN, or INR >1.5. Otherwise, may continue dosing Otherwise, may continue dosing with biweekly^d monitoring including hematology, with biweekly^d monitoring with biweekly^d monitoring biochemistry, LFT, and including hematology, including hematology, biochemistry, LFT, and coagulation coagulation per Table 10. If biochemistry, LFT, and elevation persists for ≥ 2 months, per Table 10. If elevation persists coagulation per Table 10. If must discuss with the study for >2 months, must discuss with elevation persists for ≥ 2 months, Medical Monitor before must discuss with the study the study Medical Monitor before Medical Monitor before continuing dosing. continuing dosing. continuing dosing. $>5\times$ to $8\times$ Discontinue dosing when ALT Hold[€] dose if ALT >5×ULN ULN or >5×ULN if patient is symptomatic^C, until ALT ≤1.5×ULN. Baseline TBL $>2\times$ ULN or INR >1.5. Monitoring at least weekly until ALT declining on two Otherwise, biweekly^d monitoring consecutive draws, then including hematology, biochemistry, monitoring biweekly^d, including LFT, and coagulation per Table 10. hematology, biochemistry, and If elevation persists for ≥ 2 months, coagulation per Table 10. must discuss with the study Medical Monitor before continuing dosing. Discontinue dosing after confirmation >8× ULN or Discontinue dosing after Discontinue dosing after Discontinue dosing after if ALT $> 8 \times ULN$. Baseline confirmation if ALT >8×ULN confirmation if ALT >8×Baseline confirmation if ALT or >500 U/L (whichever comes >8×Baseline or >500 U/L first). (whichever comes first).

Abbreviations: ALT=alanine aminotransferase; INR=international normalized ratio; TBL=total bilirubin; ULN=upper limit of normal Note: In addition to these criteria, other assessments or evaluations may be performed per Investigator discretion, as appropriate.

- c Symptoms of liver injury (eg, nausea, right upper quadrant pain, jaundice).
- d The frequency of laboratory monitoring should be decreased from biweekly to monthly once ALT has decreased to \leq 1.5 × ULN or \leq 1.5 × Baseline (whichever is higher).
- e After dosing is held, once ALT has decreased to ≤1.5×ULN or ≤1.5×Baseline (whichever is higher), re-dosing may be considered. In patients with normal Baseline ALT, permanently discontinue dosing if ALT increases to >5×ULN following repeat dosing. In patients with elevated Baseline ALT, permanently discontinue dosing if ALT increases to >5×Baseline or >300 U/L (whichever comes first) following repeat dosing.

a If multiple baseline ALT measurements are available, Baseline ALT will be defined as the average of the 2 most recent ALT measurements prior to first dose administered in parent study (ALN-AT3SC-001); if these two measurements differ by >50%, the average of the 3 most recent ALT measurements will be utilized (if available).

b In HCV RNA positive patients with elevated Baseline ALT whose ALT normalizes after successful DAA treatment (with SVR), Baseline ALT should be considered reset to the new normalized value and the stopping rules for HCV RNA negative patients with normal Baseline ALT should be applied going forward.

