Study assessments will be performed as specified in the Schedule of Assessments (Table 1, Table 2, and Table 3). Fitusiran dosing may occur at home in patients who are trained on self-administration. For up to 2 years, all fitusiran dosing administered at the study center or at home, LFT results are to be obtained within 7 days prior to dosing and results are to be reviewed prior to each dose. From Year 3 onwards, the frequency of predose LFT monitoring may be decreased for patients who have negative hepatitis C antibody titers and meet the following criteria for reduced predose LFT monitoring:

- a) Did not have any ALT elevation $>3 \times$ ULN persisting for ≥ 2 months at any time during the previous 12 months.
- b) Did not have any fitusiran doses held due to LFT elevations during the study.

After any modification to the dosing regimen:

- a) Did not have any ALT elevation >3× ULN persisting for ≥2 months at any time during the first 12 months under this regimen
- b) Must not have had any fitusiran doses held during the first 12 months under this regimen Safety and efficacy assessments will be performed at the clinical study center at each clinic visit and during an End of Treatment visit. Patients will return to the clinical study center for an End of Study visit 30 days after the last dose of study drug. Separately, follow-up visits to assess AT activity levels should occur at approximately monthly intervals until AT activity level returns to approximately 60% (per the central laboratory), or per Investigator discretion in consultation with the study Medical Monitor (Note: for patients who opt for the commercially available fitusiran, these follow-up visits to assess AT activity level are not required).

Pharmacokinetic assessments will be performed on Day 1, at the Month 12 visit, and at the Month 24 visit (in a subset of patients). Patients will also return to the clinical study center on Day 2 and the day after the Month 12 and Month 24 (in a subset of patients) visits for further PK sampling. Pooled urine collection will also occur at the Month 24 visit in a subset of patients.

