- a This schedule applies for patients meeting criteria for adjusted dosing regimen. Upon each dose adjustment, the patient will restart the schedule (For dose adjustment from 50 mg Q2M to 50 mg QM, the patient will restart at PR M1 as their Month 6 visit under 50 mg will serves as their PR Study Day 1. For dose adjustment from 50 mg QM to 80 mg QM, the patient will restart at PR Study Day 1). The duration that the patient must continue in the study post modified IMP dose/frequency re-start depends on the re-start time-point relative to the overall study start for each individual patient to ensure an overall duration of fitusiran administration of approximately 72 months or 18 calendar months after restarting dosing post dosing pause (whichever is longer). Thus, when the patient reaches the latter of 72 months of study participation or 18 calendar months post dosing restart, the EOT visit should be performed, followed by the EOS and AT follow-up period.
- b Patients will follow either the Q2M or QM dosing regimen according to the dose adjustment rules; see Section 6.5.1.3. SC administration of study drug as per Pharmacy Manual. From Year 3 onwards, the frequency of predose LFT monitoring may be decreased for patients who have negative hepatitis C antibody titers and meet specific criteria defined in Section 6.5.1.1.
- c On Day 1, a directed physical examination will be performed at predose and 6 hours postdose. On all other dosing days checked in the table, the directed physical examination will be performed predose. See Section 9.1.5 for assessments to be performed during a directed physical examination.
- d Vital signs include blood pressure, heart rate, body temperature (oral, tympanic, or axillary), and respiratory rate. Vital signs will be measured in the seated or supine position after the patient has rested comfortably for 10 minutes. On Day 1, vital signs will be collected predose and at 6 hours (±30 minutes) postdose. On all other dosing days checked in the table, vital signs will be collected predose.
- e 12-lead ECGs will be performed in the supine position after the patient has rested comfortably for 10 minutes. 12-lead ECGs will be performed before blood sample collection.

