- f Full Hepatic Tests (Table 9) Sample must be performed in all patients once, at Screening (if newly enrolled) or at next scheduled clinic visit (if patient has already completed a clinic visit) and annually thereafter. FibroScan (or FibroTest with APRI) testing must be performed in all patients found to have positive hepatitis C antibody titers
- g As determined by Nijmegen modified Bethesda assay.
- h Blood samples will be collected predose at visits checked in the table. Biochemistry, hematology, and coagulation are described in Section 9.1.7.1.

- i LFT testing is not required at these visits for patients on the every other month dosing regimen or for patients who meet the criteria for every other month pre-dose LFT monitoring with dosing described in Section 6.5.1.1
- j Sample for urinalysis will be collected predose at visits checked in the table. Urinalysis parameters are described in Section 9.1.7.3.
- k Blood samples will be collected predose at visits checked in the table. ADA samples will be collected within 240 minutes before dosing according to the schedule in Table 15 and Table 16. At each dose level, upon the first AT activity level <15%, the patient must have another AT activity level sample drawn within 1 week of site receipt of the result.
- / Assessments will be performed predose at visits checked in the table, where available.
- m To be completed once, prior to dosing with fitusiran.
- n Will include review of entries, (symptoms of bleed events, bleed causality, bleed severity, factor or BPA doses administered), whether site contact occurred regarding treatment of bleeds, and review of patient bleed management plan and recommendations and requirements for site contact regarding dosing.
- o Perioperative assessment of safety and hemostatic efficacy only in patients undergoing major operative procedures while on study (see Table 4).
- p AEs including signs and symptoms of thrombosis will be evaluated continuously (see Section 5.5).
- q Medication(s) will be recorded as concomitant if any of the following apply: 1) medication is ongoing from a previous fitusiran clinical trial; 2) medication started between a previous fitusiran clinical trial and the present study; or 3) medication started after signing informed consent for the present clinical trial.

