1.3.3 Summary of Pharmacokinetic and Pharmacodynamic Effects in ALN-AT3SC-001 and ALN-AT3SC-002

Consistent with the intended pharmacological effects, regardless of inhibitor status, fitusiran dose-related reductions in AT activity level have been observed in the clinical studies and have been associated with increased thrombin generation. In Part C of the Phase 1 study, the mean maximum AT activity level reductions following 3 monthly doses of 0.225, 0.45, 0.9 or 1.8 mg/kg fitusiran were 70% (N=3), 77% (N=3), 77% (N=3), and 89% (N=3), respectively. A fixed dose, 80 mg fitusiran, was also explored in Part C, resulting in a mean maximum AT activity level reduction of 87% (N=6). In Part D of the study, patients with inhibitors were dosed with 50 or 80 mg fitusiran and experienced mean maximum AT activity level reduction of 82% (N=6) and 87% (N=11), respectively. AT reduction was maintained in this study (ALN-AT3SC-002), with mean maximal AT reduction of 83.6% for 50 mg (N=13) and 85.9% for 80 mg (N=21) as of 08 August, 2017.

Consistent with the therapeutic hypothesis, increased AT lowering in patients with hemophilia resulted in increased thrombin generation when AT lowering was in the highest quartile (>75%) compared to when AT lowering was in the lowest quartile (<25%). Further, the peak thrombin generation values achieved with AT lowering of >75% were comparable to those in the lower end of the normal range observed in healthy individuals. None of the thrombin generation measurements following >75% AT reduction in hemophilia patients exceeded those seen in healthy males.

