6.5.1.3 Antithrombin level criteria for a dose adjustment

With the introduction of the new dose and regimen with Protocol Amendment 07 following the global program dosing pause implemented by Sponsor in 2020, patients will receive fitusiran treatment according to the below antithrombin level scenarios and criteria. See the rationale for a new dosing justification in Section 1.5. Dose modification rules are detailed in the section below and displayed in Figure 1 and Figure 2.

A) Dose restart

- a) Restart at 50 mg Q2M
- Patients that reach AT activity levels ≥22% (per central laboratory),
- Patients previously exposed to fitusiran at a dose of 50 mg QM or 80 mg QM with more than one AT activity level <15% (per central laboratory) at any time during fitusiran treatment,
- Patients will resume dosing at a dose of 50 mg Q2M and follow the modified IMP regimen SoAs (Table 3).
- b) Restart at 50 mg QM or 80 mg QM (prior dose)
- Patients that reach AT activity levels ≥22% (per central laboratory),
- Patients previously exposed to fitusiran at a dose of 50 mg QM or 80 mg QM with no more than one AT activity level <15% (per central laboratory) at any time during fitusiran treatment (based on at least 3 months of prior AT measurements),
- Participant may have the option to remain on that dose and follow the SoAs in Table 1 and Table 2.

B) Dose escalation

- a) Dose escalation to 50 mg QM
- After a period of dosing at 50 mg Q2M,
- Based on 2 steady state AT values >35% at the 50 mg Q2M dosing regimen,

- At least 2 of the 3 AT samples taken pre-dose at PR Month 4, PR Month 5 and PR Month 6 must be >35% to meet the escalation rule,
- Patients who previously had more than 1 AT value <15% at the 50 mg QM dose are not eligible to re-escalate to this dose level,
- If escalation rules are met, patient will receive the 50 mg dose at PR Month 7 (this will be considered the PR Month 1 of 50 mg QM, ie, the second 50 mg QM dose).

Note: If any of the doses prior to PR Month 6 are missed, then the decision-making for escalation must be shifted accordingly.

- b) Dose escalation to 80 mg QM
- After a prior escalation to the 50 mg QM dosing regimen,
- Based on 2 steady state AT values >35% at the 50 mg QM dosing regimen,

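### Protocol 6.5.1.1 item 3 leaves out the hepatitis C condition for reduced predose liver tests in patients escalated to monthly dosing, which Table 3 footnote b, Sections 3.1 and 6.5 and the synopsis all require

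*Protocol*

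**What the plan says.** Section 6.5.1.1 splits the rule by schedule. Item 2, for Tables 1 and 2, allows fewer predose LFTs from Year 3 in hepatitis C negative patients who meet two further criteria. Its Note counts antibody-positive patients without detectable virus as negative, but "patients who cleared Hep C infection must have documented sustained negative virologic load".

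Item 3, for monthly dosing under Table 3, says that "monthly predose LFT testing is not required if the criteria for reduced predose LFT monitoring is met as described below". The two criteria below it are no ALT above 3× ULN lasting 2 or more consecutive months, and no held dose, both in the first 12 months under the regimen. It gives no hepatitis C condition, start time or interval.

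Table 3 footnote b, on the dosing rows, reads: "From Year 3 onwards, the frequency of predose LFT monitoring may be decreased for patients who have negative hepatitis C antibody titers", and adds the criteria of 6.5.1.1. Sections 3.1 and 6.5 carry the same condition. The synopsis limits the reduction to patients "who have negative hepatitis C antibody titers and meet the following criteria for reduced predose LFT monitoring", and lists the criteria for a modified regimen under that lead-in. Table 3 footnote i, on the LFT row, waives the marked visits for "patients who meet the criteria for every other month pre-dose LFT monitoring with dosing described in Section 6.5.1.1" and does not mention hepatitis C.

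**The concern.** Item 3 is written for one group of patients, refers to criteria set out below it, and reads as complete. Footnote i, which tells a site whether a test is due at a given visit, sends the reader only to 6.5.1.1. A site working from those two places would find no hepatitis C condition, because both the condition and its defining Note sit under item 2, for Tables 1 and 2.

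The protocol expects such patients. Exclusion criterion 1 bars only known hepatitis C that currently requires ribavirin or interferon. Table 9 has columns for HCV RNA positive patients. SAP Section 6.8.2 says that hepatitis C infected participants entered the parent study, and analyses ALT or AST elevations above 3× ULN by HCV status. At stake is the check that lets the Table 9 rules act before a dose is given rather than after it.

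**Working it through.** **1. The texts side by side**

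| Text | Applies to | Hepatitis C negative required? | Start | Interval |
|---|---|---|---|---|
| 6.5.1.1 item 2b | Tables 1 and 2 | Yes | Year 3 | not given |
| 6.5.1.1 item 3 | Table 3, monthly | **No** | not given | not given |
| 6.5.1.1 item 4 | Table 3, every 2 months | No | after first year | before every dose |
| Table 3 footnote b | Table 3, dosing rows | Yes | Year 3 | not given |
| Table 3 footnote i | Table 3, LFT row | No; points to 6.5.1.1 | marked visits | every other month |
| 3.1, 6.5, synopsis | not limited to one schedule | Yes | Year 3 | not given |

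**2. Test case.** Take a viraemic patient on escalated monthly dosing who meets both item 3 criteria. Item 3 with footnote i waives alternate tests. Footnote b, 3.1, 6.5 and the synopsis do not allow it. The same patient gets opposite answers.

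**3. Who this can be.** Patients who restart at their prior monthly dose follow Tables 1 and 2 (6.5.1.3 A b), so monthly patients on Table 3 are those escalated from 50 mg every 2 months. Under 6.5.1.3 B a, "Patients who previously had more than 1 AT value <15% at the 50 mg QM dose are not eligible to re-escalate" to that dose, so the group is mainly former 80 mg patients. No document gives its size. For scale only, Section 1.3.3 reports mean maximal AT reduction of "83.6% for 50 mg (N=13) and 85.9% for 80 mg (N=21) as of 08 August, 2017", which is 13 + 21 = 34 patients.

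**4. Tests per patient.** Assumptions:
- Restart on 27 January 2021, the day after the date in SAP Table 4.
- Escalation to 50 mg monthly at the first opportunity.
- End of treatment no earlier than 18 calendar months after restart: 27 July 2022, day 547.
- End of treatment no later than study day 2161 for entry on 20 July 2017, the parent study's last visit (SAP 2.1). 20 July 2017 + 2160 days = 19 June 2023, day 874.

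SAP Table 2 places monthly visit PRMk at PR Month k + 6, which is day 28 × (k + 6) + 1. Continuing that rule past the end of the table:
- PRM13: 28 × 19 + 1 = 533
- PRM14: 28 × 20 + 1 = 561
- PRM25: 28 × 31 + 1 = 869
- PRM26: 28 × 32 + 1 = 897
- PRM27: 28 × 33 + 1 = 925

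| Waiver starts at | Treatment ends day 547 | Treatment ends day 874 |
|---|---|---|
| PRM25 (Year 3 of Table 3, which restarts at each dose adjustment) | 0 | 1 (PRM25) |
| PRM13 (after 12 months under the regimen) | 1 (PRM13) | 7 (PRM13, 15, 17, 19, 21, 23, 25) |

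In the public text, the legible footnote i marks on the LFT row fall at PRM27, PRM29 and PRM33, all in Year 3. PRM27 (day 925) is already past day 874. Superscripts may have been lost in extraction, so nothing is inferred from the unmarked visits.

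**The case against.** The strongest reply is that this is non-repetition rather than conflict. Footnote b belongs to the schedule these patients follow, and it joins two requirements: hepatitis C negativity, and the criteria of 6.5.1.1. Item 3 can be read as supplying only the second. The synopsis confirms that order, and no text says outright that a hepatitis C positive patient may have fewer tests. This stands in part: a site that reads footnote b with item 3 will apply the condition. It does not remove the defect, because neither item 3 nor footnote i sends the reader to footnote b.

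The objection on size stands. The figure of 7 combines early restart, first-opportunity escalation and late entry with a start at PRM13, which conflicts with footnote b's Year 3. If only the legible marks count, no test falls before day 874. Safeguards also remain: 12 clean months are needed first, any held dose bars the reduction, LFTs continue every other month, Table 9 still applies, and annual hepatic tests continue, with FibroScan (or FibroTest with APRI) for antibody-positive patients.

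A reader might infer more than the documents support:
- *That every antibody-positive patient is exposed.* The Note to item 2 counts documented clearance as negative.
- *That patients dosed every 2 months are exposed.* Item 4 keeps an LFT before each of their doses.
- *That the protocol deliberately drops the condition for the new regimen.* The synopsis lists the modified-regimen criteria under the hepatitis C lead-in.

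**Conclusion.** The point holds as an inconsistency in a safety rule. Item 3 with footnote i permits a reduction that four other places withhold from the same patient. Its practical size is small. The patient must be viraemic or lack documented clearance, must have escalated to monthly dosing, and must have 12 clean months on it. The number of such patients is not given and may be zero. Under the stated dates, about 0 to 1 predose tests per patient are affected if the waiver starts in Year 3 of Table 3. Up to about 7 are affected only if item 3 is read alone, as starting after 12 months. The entry, restart and escalation dates are assumptions, since no patient's dates are given. Nothing here shows that a test was in fact missed or that any planned analysis is affected. The change is worth making because it is cheap and restores what the rest of the protocol already requires.

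**What to change.** In 6.5.1.1 item 3, add as the first criterion: *hepatitis C negative, as defined in the Note to item 2*. The cross-reference also carries the Note's treatment of cleared infection over to Table 3. In the same item, state the every-other-month interval from footnote i and the Year 3 start (PRM25) from footnote b, and check that the footnote i marks on the LFT row agree. Keep the condition where it already stands in footnote b, 3.1, 6.5 and the synopsis.

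The cost is one criterion and one sentence, or a clarification letter to sites. Each affected hepatitis C positive patient has about 6 more LFTs per 12 monthly doses (12 − 6). For other patients, the stated start asks for nothing beyond footnote b. At a site that now begins the waiver after 12 months, it would restore the six alternate tests from PRM13 to PRM23.
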